7.1. Time and Events Table

7.1.1. Screening

Procedures	Screening up to 28 days prior to day 1
Informed Consent	Х
Demographics	Х
Eligibility	Х
Full Physical Exam	Х
Medical/Medication/Drug/Alcohol Hx	Х
12-lead ECG (triplicate)	Х
Vital Signs	Х
Urine Drug/Alcohol	Х
HIV, Hep B and Hep C Screen ¹	Х
Haem/Chem/Urinalysis Tests/UPCR	Х
Concomitant Medication Review	Х
1 If test performed within 3 months prior treatment, testing at screening is	

RES117169

7.1.2. Scanning & Dosing

Day of study	Day - 1			D	ay 1				Day 6	Day 13 ± 1 day	Day 20 ± 2 days	Day 31 ± 2 days	
Time post dosing		Pre-dose	0	1 hour	3 hours	6 hours	8 hours	24 hours					
Admission to Unit	Х												
Brief Physical Exam	Х							Xa					
Medical/Medication/Drug/Alcohol Hx	Х												
12-lead ECG		Xf		Х				Х					
Vital Signs		Х		Х				Х					
Urine Drug/Alcohol	Х												
Urinalysis	Х							Xi		Х	Х	Х	
Spot Urine Protein/Creatinine ratio	Х							Xe			Х		
Haematology								Х				Х	
Clinical chemistry	Х							Х		Х	Х	Х	Х
Randomisation	Х												
Immunogenicity Blood Sample		Х											
IV Infusion Dosing			Х										
PET imaging and co-localising CT (first subject) ^a				x		х		Х		Х			
PET imaging and co-localising CT (second subject) ^a					Х		Х		Х	Х			
PET imaging and co-localising CT (subsequent subjects) ^{a, b}				←					>	•			
PK Blood Sampling for MS		Х		Х	Х	Х	Х	Х	Х	Х	Х	Х	Х
PK Blood Sampling for scintillation counting ^h		Х		x	х	х	х	Х	Х	Х	Х		
Bladder Void ^c		Х											
Urine Collection ^d				←				>					

2014N202021_00

CONFIDENTIAL

RES117169

Day of study	Day - 1	Day 1						Day 2	Day 4	Day 6	Day 13 ± 1 day	Day 20 ± 2 days	Day 31 ± 2 days
Time post dosing		Pre-dose	0	1 hour	3 hours	6 hours	8 hours	24 hours					
Adverse Event Review				←								`	
Concomitant Medication Review		←→										>	
Discharge								Х					
Outpatient Visit									Х	Х	Х	Х	Х
 a. Each PET/CT scan must be preceded b. For subsequent subjects (3rd and bey post injection. A maximum of 4 PET s c. Pre-dose urine will not be retained. d. 24 hour urine collection. Total volume stored for later MS PK analysis if reque e. Aliquot from 24 hr collection sample, t f. Triplicate measurement g. Prior to discharge 	yond) tim cans wil will be r uired. Ba	nings of PET I be conducte measured. Pa used on data	scans v ed in ea art of uri from firs	vill be base ch subject ine sample st 2 subjec	ed on data a	d for scintil	lation coun	ting. An aliqu	iot will be	utilized f	or UPCR assessme		

h. Aliquot from MS PK blood samplei. Urine sample to be collected prior to discharge i.

Note: all time points are relative to start of infusion administration.

CONFIDENTIAL

RES117169

7.1.3. Follow-up

Procedure	Day 43 ± 2 days
Brief Physical Exam	Х
12-lead ECG	Х
Vital Signs	Х
Haem/Chem/Urinalysis Tests/UPCR	Х
Immunogenicity Sample	Х
PK Sample for MS	Х
Concomitant medication review	Х
Adverse Event Review	Х
Outpatient Visit	Х

7.2. Screening and Critical Baseline Assessments

The following demographic parameters will be captured: year of birth, race and ethnicity.

Medical/medication/alcohol history will be assessed as related to the eligibility criteria listed in Section 5.1 and Section 5.2.

7.3. Safety

Planned time points for all safety assessments are listed in the Time and Events Tables. Additional time points for safety tests (such as vital signs, physical exams and laboratory safety tests) may be added during the course of the study based on newly available data to ensure appropriate safety monitoring.

7.3.1. Adverse Events (AE) and Serious Adverse Events (SAEs)

The definitions of an AE or SAE can be found in Appendix 3.

The investigator and their designees are responsible for detecting, documenting and reporting events that meet the definition of an AE or SAE.

7.3.1.1. Time period and Frequency for collecting AE and SAE information

- AEs and SAEs will be collected from the start of Study Treatment until the followup visit at the time points specified in the Time and Events Table (Section 7.1).
- Any SAEs assessed as related to study participation (e.g., protocol-mandated procedures, invasive tests, or change in existing therapy) or related to a GSK product will be recorded from the time a subject consents to participate in the study up to and including any follow-up contact.
- All SAEs will be recorded and reported to GSK within 24 hours, as indicated in Appendix 3.
- The investigator will be required to confirm review of the SAE causality by ticking the 'reviewed' box at the bottom of the electronic Case Report Form (eCRF) page within 72 hours of submission of the SAE.
- Investigators are not obligated to actively seek AEs or SAEs in former study subjects. However, if the investigator learns of any SAE, including a death, at any time after a subject has been discharged from the study, and he/she considers the event reasonably related to the study treatment or study participation, the investigator must promptly notify GSK.

NOTE: The method of recording, evaluating and assessing causality of AEs and SAEs plus procedures for completing and transmitting SAE reports to GSK are provided in Appendix 3.

7.3.1.2. Method of Detecting AEs and SAEs

Care will be taken not to introduce bias when detecting AEs and/or SAEs. Open-ended and non-leading verbal questioning of the subject is the preferred method to inquire about AE occurrence. Appropriate questions include:

- "How are you feeling?"
- "Have you had any (other) medical problems since your last visit/contact?"
- "Have you taken any new medicines, other than those provided in this study, since your last visit/contact?"

7.3.1.3. Follow-up of AEs and SAEs

After the initial AE/SAE report, the investigator is required to proactively follow each subject at subsequent visits/contacts. All SAEs will be followed until resolution, until the condition stabilizes, until the event is otherwise explained, or until the subject is lost to follow-up (as defined in Section 5.4). Further information on follow-up procedures is given in Appendix 3.

7.3.1.4. Regulatory Reporting Requirements for SAEs

Prompt notification by the investigator to GSK of SAEs and non-serious AEs related to study treatment (even for non- interventional post-marketing studies) is essential so that legal obligations and ethical responsibilities towards the safety of subjects and the safety of a product under clinical investigation are met.

GSK has a legal responsibility to notify both the local regulatory authority and other regulatory agencies about the safety of a product under clinical investigation. GSK will comply with country specific regulatory requirements relating to safety reporting to the regulatory authority, Institutional Review Board (IRB)/Independent Ethics Committee (IEC) and investigators.

Investigator safety reports are prepared for suspected unexpected serious adverse reactions according to local regulatory requirements and GSK policy and are forwarded to investigators as necessary.

An investigator who receives an investigator safety report describing a SAE(s) or other specific safety information (e.g., summary or listing of SAEs) from GSK will file it with the IB and will notify the IRB/IEC, if appropriate according to local requirements.

7.3.2. Pregnancy

Details of all pregnancies in female partners of male subjects will be collected after the start of dosing and until the follow-up visit.

If a pregnancy is reported then the investigator should inform GSK within 2 weeks of learning of the pregnancy and should follow the procedures outlined in Appendix 4.

7.3.3. Physical Exams

- A complete physical examination will include assessments of the head, eyes, ears, nose, throat, skin, thyroid, neurological, lungs, cardiovascular, abdomen (liver and spleen), lymph nodes and extremities. Height and weight will also be measured and recorded.
- A brief physical examination will include assessments of the skin, lungs, cardiovascular system, and abdomen (liver and spleen).
- A full physical examination will be conducted at screening and a brief physical exam will be conducted on Day -1, at 24 hr post dose prior to discharge and at Follow-up.

7.3.4. Vital Signs

- Vital sign measurements will include systolic and diastolic blood pressure, pulse rate, and temperature.
- All vital sign measurements will be made with the subject in a supine position having rested in this position for at least 5 minutes before each reading.

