4.4. Risk Assessment and Management

Summaries of findings from non-clinical studies conducted with GSK3128349 can be found in the GlaxoSmithKline Document Number 2014N199359_00 Investigator Brochure. Although GSK3128349 was well tolerated in a rat toxicology study, it has not been tested in humans before therefore potential adverse affects may be encountered. The table below summarises the potential key risks and mitigation strategy for this protocol.

Table 3Summary of protocol-specific risks and mitigation strategies

Potential risk	Summary of data	Impact- eligibility criteria	Strategy-monitoring/stopping criteria			
Renal injury	The AlbudAb platform has been associated with degenerative changes in the proximal renal tubule in the mouse with repeat and long duration (greater than 4 weeks) dose regimen only. These observations appear reversible on washout and have not been observed in monkey safety studies (see summary Section 4.3 and IB for detailed information).	Subjects with history of renal disease and/or abnormalities are excluded, including proteinuria and reduced estimated Glomerular Filtration Rate (eGFR) (see exclusion criteria Section 5.2 points 3, 11 and 12 for more information).	Renal function and proteinuria will be closely monitored using standard serum and urine chemistry biomarkers.			
Acute infusion reaction	Infusion / acute allergic reactions upon administration are a potential risk with all protein therapeutics.	Subjects are excluded with a history of sensitivity to any of the study treatment, or components thereof or a history of drug or other allergies.	Subjects will be monitored for symptoms of hypersensitivity or other potentially immune- mediated reactions post-infusion, and will be treated promptly as appropriate.			
Immunogenicity	As is the case for all protein therapeutics, antibodies may develop against the agent administered.	None	Immunogenicity samples will be drawn at baseline and following dosing of GSK3128349 to monitor the immunogenicity potential of this molecule.			
Radioactivity exposure	The total radioactivity exposure due to combined PET ligand	Subjects with previous involvement in a research	After completion of the first 2 subjects, dosimetry analysis will			

2014N202021_00

CONFIDENTIAL

Potential risk	Summary of data	Impact- eligibility criteria	Strategy-monitoring/stopping criteria

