6. STUDY TREATMENT

The term 'study treatment' or ⁽⁸⁹Zr-GSK3128349' is used throughout the protocol to describe the drug product, which is a mix of ⁸⁹Zr labeled and unlabelled GSK3128349 received by the subjects as per the protocol design. Details of ⁸⁹Zr labelled GSK3128349 can be found in the relevant non Investigational Medicinal Product (IMP) document.

Product name:	⁸⁹ Zr-GSK3128349						
Formulation	50 mM sodium acetate buffer and 200 mM sucrose at pH						
Description:	5.20-5.80, associated with about 15 MBq of radioactivity.						
Dosage Form:	Solution for IV administration						
Unit Dose	Approximately 10 mL of 0.1mg/mL ⁸⁹ Zr-GSK312834						
Strength							
Dose level	1 mg						
Route/	IV as a continuous infusion over 20 mins						
Administration/							
Duration:							
Dosing	Single dose						
Instructions:							
Physical	Liquid in 50mL vial						
Description:							
Manufacturer/	VUMC, Amsterdam						
Source of							
procurement:							

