6.4. Preparation/Handling/Storage/Accountability

A full description of the method and materials required for administration of ⁸⁹Zr-GSK3128349 will be provided in the Study Reference Manual (SRM).

Study treatment must be dispensed or administered according to procedures described in the SRM. Only subjects enrolled in the study may receive study treatment. Only authorized site staff may supply or administer study treatment. All study treatment must be stored in a secure area with access limited to the investigator and authorized site staff. Storage instructions for all study treatments supplied by GSK (including study product as well as prepared solutions) are provided in the SRM. Maintenance of a temperature log (manual or automated) is required.

Under normal conditions of handling and administration, study treatment is not expected to pose significant safety risks to site staff. Take adequate precautions to avoid direct eye or skin contact and the generation of aerosols or mists. In the case of unintentional occupational exposure notify the monitor, Medical Monitor and/or GSK study contact.

A Material Safety Data Sheet (MSDS)/equivalent document describing occupational hazards and recommended handling precautions either will be provided to the investigator, where this is required by local laws, or is available upon request from GSK.

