7. STUDY ASSESSMENTS AND PROCEDURES

Protocol waivers or exemptions are not allowed with the exception of immediate safety concerns. Therefore, adherence to the study design requirements, including those specified in the Time and Events Table, are essential and required for study conduct.

This section lists the procedures and parameters of each planned study assessment. The exact timing of each assessment is listed in the Time and Events Table Section 7.1. Detailed procedures for obtaining each assessment may be provided in the Study Reference Manual (SRM), where necessary. Whenever vital signs, 12-lead ECGs and blood draws are scheduled for the same nominal time, the assessments should occur in the following order: 12-lead ECG, vital signs, blood draws. The timing of the assessments should allow the blood draw to occur at the exact nominal time.

The timing and number of planned study assessments, including: safety, pharmacokinetic or pharmacodynamic/biomarker assessments may be altered during the course of the study based on newly available data (*e.g.* to obtain data closer to the time of peak plasma concentrations) to ensure appropriate monitoring. The timing of PET-CT scans may be changed but not the maximum number of four PET-CT sessions. The change in timing or addition of time points for any planned study assessments must be approved and documented by GSK, but this will not constitute a protocol amendment. The Institutional Review Board (IRB)/ Independent Ethics Committee (IEC) will be informed of any safety issues that require alteration of the safety monitoring scheme. No more than 500 mL of blood will be collected within a 56 day period as per exclusion criteria 19 (Section 5.2), including any extra assessments that may be required.

RES117169

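### Acute infusion reaction is a named risk of this first-in-human 20-minute infusion, yet the first post-dose vital signs scheduled for all subjects fall nominally 40 minutes after it ends (minor; cheap to improve)

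*Protocol*

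**What the plan says.** Protocol section 4.4 says of the molecule that "it has not been tested in humans before". Table 3 in that section includes acute infusion reaction: "Infusion / acute allergic reactions upon administration are a potential risk with all protein therapeutics". The mitigation is clinical: "Subjects will be monitored for symptoms of hypersensitivity". It applies after the infusion, with prompt treatment, and gives no times or readings.

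Protocol section 6 gives the route as "IV as a continuous infusion over 20 mins". Section 7.3.4 sets the content of a reading ("Vital sign measurements will include systolic and diastolic blood pressure, pulse rate, and temperature") and requires five minutes of supine rest, but gives no times. Those are in the Time and Events table, section 7.1.2. There the row "IV Infusion Dosing" is marked at time 0, and the Vital Signs row is marked at pre-dose, 1 h and 24 h, with no column between 0 and 1 h. A note states that times run from the start of infusion. SAP section 10.2.1 repeats the same row and note. Footnote a adds heart rate and blood pressure before each PET/CT scan.

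**The concern.** A reaction to a protein infusion is most naturally looked for during the infusion and just after it. The protocol itself places this risk at administration. Vital signs are also a listed endpoint of secondary objective 2.4, safety and tolerability. Yet the schedule takes no reading for the whole cohort between pre-dose and 1 h.

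Ad hoc readings would not fully replace a planned one. SAP section 10.3.3 keeps unscheduled visits out of summary tables and figures. It sends unscheduled readings to listings, but the only vital-sign listings planned (22 and 23) are for subjects with a value beyond the limits in SAP section 10.6.3. At stake is a small piece of planned, comparable safety data across 6 to 8 subjects.

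**Working it through.** The plan states no figure for this gap, so there is none to reproduce. The check is timing arithmetic.

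**Inputs**
- Infusion length: 20 min (Protocol section 6).
- First post-dose vital signs for all subjects: 1 h, or 60 min, from infusion start (Protocol section 7.1.2; SAP section 10.2.1).
- First PET scans: subject 1 at 1 h ± 30 min and subject 2 at 3 h ± 30 min, counted from completion of infusion (Protocol Table 1). The Time and Events note counts from the start instead, so both are shown.
- Cohort: 6 to 8 subjects.

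**Gap after the infusion**
- 60 - 20 = 40 min.
- If 1 h were counted from the end of infusion, against the table note, the gap would be 60 min.
- Protocol section 7 says that, at a shared nominal time, "the assessments should occur in the following order: 12-lead ECG, vital signs, blood draws", with the blood draw at the exact time. The 1 h reading may therefore come slightly before 60 min, so 40 min is nominal.

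**Could the pre-scan checks close it?** Scan times in minutes after the end of infusion:

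| Subject | Counted from completion | Counted from start (subtract 20) |
|---|---|---|
| 1 | 60 ± 30 = 30 to 90 | 10 to 70 |
| 2 | 180 ± 30 = 150 to 210 | 130 to 190 |
| 3 onward | not fixed | not fixed |

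The check precedes the scan by an unstated interval and does not include temperature. Subject 1 may have one before the 1 h set, and later subjects possibly so. For no subject is it tied to the end of infusion.

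**Scheduled sets**
- Now: screening 1 + pre-dose, 1 h and 24 h 3 + Day 43 follow-up 1 = 5 per subject; 6 × 5 = 30 to 8 × 5 = 40 in the cohort. During or at the end of infusion: 0.
- With one added: 6 per subject; 6 × 6 = 36 to 8 × 6 = 48.
- Difference: 6 to 8 readings.

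**The case against.** The strongest reply is that the named risk already has a suitable mitigation. A reaction is recognised from symptoms and individual observation, not from a cohort mean blood pressure. Subjects are resident from Day -1 until 24 h after dosing. Adverse events are collected from the start of treatment (Protocol section 7.3.1.1), and Appendix 3 counts a clinically significant vital-sign change as one. An ad hoc blood pressure or heart rate value beyond the SAP limits would reach Listings 22 and 23. Time points can be added. The dose is a single 1 mg, with a 26-fold predicted Cmax margin, and the protocol rates the risk as quite low. No rule in the documents is broken.

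Most of this stands, and it makes the point minor. It does not supply a planned reading in the window. The provisions for adding time points (Protocol sections 7 and 7.3) are discretionary and worded for newly available data.

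A reader might infer that subjects are unobserved during the infusion. The documents do not support that. Protocol section 6.4 says of the Study Reference Manual that it will hold "A full description of the method and materials required for administration". That manual is not among the documents and may describe bedside observation. Such observation would not by itself put a reading in the schedule or the summaries.

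A reader might also infer that the 1 h set misses peak exposure, since Table 2 models Cmax at t=0. That does not follow. Protocol section 2.1 gives albumin exchange of 4-5% of total per hour, with the extravascular pool about twice the intravascular, so about one third is in plasma. If the drug follows albumin, 4-5% ÷ 1/3 = 12-15% of the plasma pool leaves per hour, or 12-15% × 40/60 = 8-10% in 40 min. Exposure at 1 h would still be about 90% of peak, and nothing in the documents ties hypersensitivity to Cmax.

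**Conclusion.** The point holds as a minor improvement. For all subjects, no vital-sign set is scheduled during or at the end of the infusion, and the first post-dose set is nominally 40 min after its end. The loss is a planned objective reading in the risk window, not the ability to detect or treat a clinically evident reaction. It would be wrong to read this as a serious safety failure. Nor can the share of transient changes missed be stated, because the documents give neither the onset nor the duration of such changes.

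The conclusion rests on the Time and Events table as reproduced in both documents, on its note that times run from the start of infusion, and on the nominal 20-minute duration.

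**What to change.** Add one Vital Signs mark to the Time and Events table at the end of infusion, about 20 min from its start, and keep the 1 h set. Give it its own planned time point in SAP Tables 4.12 and 4.13, so that it is summarised separately from 1 h.

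The cost is one more non-invasive reading per resident subject, 6 to 8 in total, with the supine rest that section 7.3.4 requires. It brings a possible incidental out-of-range value, and a brief change could still fall between readings. It is simplest to edit the table before the first subject is dosed, because the route for adding time points without an amendment may not apply in the absence of new data.

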7.3.5. Electrocardiogram (ECG)

- ECG measurements will be made with the subject in a supine position having rested in this position for at least 5 minutes before each reading.
- Triplicate 12-lead ECGS will be obtained at screening and pre dose at Day 1 and single 12-lead ECGs will be obtained at other time points during the study.
- 12-lead ECGs will be obtained using an ECG machine that automatically calculates the heart rate and measures PR, RR, QRS, QT, and QTcF intervals (if the machine does not automatically calculate QTcF, manual calculation is acceptable).
- Extreme changes in room temperature should be avoided as far as possible (the volunteers should be comfortable at all times in appropriate clothing). Hot and cold drinks and food should be avoided where possible 30 minutes before an ECG measurement.
- Care should be taken to ensure that the electrodes are placed in the positions dictated by standard ECG methodology.

If a subject's QTcF interval extends beyond 500msec on two or more ECG tracings separated by at least 5 minutes then the ECG tracing should be examined and manual measurement by a trained physician should be performed to confirm the accuracy of the equipment being used. If the reading is accurate the subject should be monitored closely and followed until the QT and QTcF interval returns to within 30msec of their baseline.

7.3.6. Clinical Safety Laboratory Assessments

Values for the laboratory parameters should be within the normal range for the relevant subject population as specified by the clinical laboratory, which will be an accredited facility. Subjects with screening laboratory values outside of the normal range will be accepted into the study only after the Investigator, or a qualified designee, and the GSK

Medical Monitor have determined that the out of range value(s) are not clinically significant and would not pose an increased risk to the subject.

At the Principal Investigator and GSK Medical Monitor's discretion, additional laboratory tests other than those outlined below may be included to further assess safety and tolerability.

Hematology, clinical chemistry, urinalysis and additional parameters to be tested are listed below:

Hematology

	8/			
Platelet Count	RBC Indices :	Automated WBC Differential:		
RBC Count	MCV	Neutrophils		
WBC Count (absolute)	МСН	Lymphocytes		
Reticulocyte Count	MCHC	Monocytes		
Hemoglobin		Eosinophils		
Hematocrit Basophils		Basophils		
RBC- Red blood cell; WBC- White Blood Cell; MCV- Mean Corpuscular Volume; MCH- Mean				
Corpuscular Hemoglobin; MCHC- Mean Corpuscular Hemoglobin Concentration.				

Clinical Chemistry

BUN	Potassium	AST (SGOT)	Total and direct bilirubin
Creatinine	Chloride	ALT (SGPT)	Uric Acid
(eGFR)			
Glucose	Calcium	GGT	Albumin
Sodium		Alkaline phosphatase	Total Protein
BUN- Blood Urea Nitrogen; AST (SGOT)- Aspartate Aminotransferase (Serum Glutamic Oxaloacetate			
Transaminase); eGFR-ALT- Alanine Aminotransferase (SGPT)- (Serum Glutamic Pyruvic Transaminase);			

GGT- Gamma Glutamyl Transpeptidase.

Routine Urinalysis

Specific gravity
pH, glucose, protein, blood and ketones by dipstick
Microscopic examination (if blood or protein is abnormal) includes RBC, WBC, casts
and bacteria

Other tests

HIV		
Hepatitis B (HBsAg)		
Hepatitis C (Hep C antibody if second generation Hepatitis C antibody positive, a		
hepatitis C antibody Chiron RIBA immunoblot assay (or other third generation		
immunoassay) should be reflexively performed on the same sample to confirm the		
result)		
Alcohol and drug screen (to include at minimum: amphetamines, barbiturates, cocaine,		
opiates, cannabinoids and benzodiazepines).		
Proteinuria (UPCR)		
NOTE :		
Details of Liver Safety Required Actions and Follow-Up Assessments after a		
liver event are given in Appendix 2.		

Additional drug screens may be performed at the discretion of site staff, if needed/required by local standard operating procedures.

All laboratory tests with values that are considered clinically significantly abnormal during participation in the study should be repeated until the values return to normal or baseline. If such values do not return to normal within a period judged reasonable by the investigator, the etiology should be identified and the sponsor notified.

